6.5 Subject Discontinuation

Following the index procedure, subjects should remain in the study until completion of required follow-up. The follow-up period for this study is 12 months (365 ± 30 days).

However, a subject's participation may be discontinued. Potential reasons for discontinuation may include, but are not limited to the following:

- Lost to Follow-Up (LTF): A subject may be considered LTF if the site personnel are unable to locate the subject despite two documented attempts to notify the subject via telephone and a third attempt by certified mail. This does not apply to missed visits, where the subject misses one of the follow up contact time points, but completed a subsequent one (when a subject misses two consecutive follow-ups with failure of contact attempt, the subject may be considered LTF and withdrawn from the study). Before the site considers a subject LTF, written agreement should be obtained from the Sponsor.
- *Withdrawn Consent:* The subject requests to terminate his/her participation in the study (the Investigator must attempt to identify and document the reasons for termination).
- *Death:* The subject becomes deceased. If known, the cause of death must be documented (see Section 8.5).
- *Withdrawal by Investigator:* Participation may be immediately terminated by the Investigator if, in the opinion of the Investigator, the subject would be exposed to inappropriate risk by continuing in the study. Additionally, the Investigator may terminate a subject's participation with prior written approval from the Sponsor if the subject is repeatedly noncompliant with study procedures.
- *Study Termination:* The study is terminated by the Sponsor (see Section 11.9).

Additional subjects will not be enrolled to replace those who withdraw from the study.

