6.4 Subject Follow-Up

All study subjects are to be followed according to the investigational site's standard of care practices. In addition to the standard of care visits, study participants will either return to the site or be reached by telephone at the following intervals:

- *Follow-up Contact 1*: 30 ± 7 days post-procedure;
- *Follow-up Contact 2:* 6 months ± 30 days post-procedure;
- *Follow-up Contact 3:* 12 months \pm 30 days post-procedure.

Subjects with a treated ATK target lesion will return to the site to undergo a Duplex Ultrasound (DUS) performed at 30 days and 6 and 12 months post-index procedure. DUS imaging of the target lesion employing the "Ultrasound Guidelines" shall be uploaded or sent to the core laboratory for analysis.

Subjects with a treated BTK target lesion will return to the site for a standard of care clinical evaluation at 30 days and 6 and 12 months post-index procedure. DUS is not required for BTK subjects.

The following will be collected during follow-up and documented in the subject's medical record at the site:

- *Documentation of Status:* Determine and document whether the subject has undergone a TLR or target vessel revascularization (TVR), amputation procedure since last contact, and antiplatelet/anticoagulation medications. Angiographic imaging of any TLR/TVR must be sent to the angiographic core lab for analysis. Measurement of target limb ABI and Rutherford Classification.
- *Documentation of AEs:* Documentation of occurrence of AEs since last followup (see Section 8).

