6.2 Freedom from TLR

Target lesion information will be obtained from 'Core Lab Analysis – Angio Re-Intervention Analysis' CRF page. If for some reason the Angio data is missing, but there was TLR reported by site then Site Re-Intervention data will be used from 'Target Vessel Re-Intervention' CRF page. Freedom from TLR will be analyzed by subject at 30 days, 6 months, and 12 months visit.

Evaluable subjects: To be included in the denominator at a particular visit, the subject should have been followed-up beyond the beginning of the lower end of the respective visit window (23 days for 30 days, 150 days for 6 months, and 335 days for the 12 months) or the subject should have had a TLR event before the upper limit of visit window (37 days for 30 days, 210 days for 6 months, and 395 days for the 12 months).

The TLR (Re-intervention date) is based on the following definition:

TLR duration = (Date of TLR - Date of Index Procedure).

Failure: Subject has a failure event if Target Lesion Re-Intervention occurred before the upper limit of the respective visit window (Core Lab Angio CRF page). If TLR was reported by site but was missing in the Core lab page, then use Target Lesion Revascularization occurred before the upper limit of the visit window (Site Re-Intervention CRF page) as failure.

Success: Subject has no failure event and is an evaluable subject as defined above.

Kaplan-Meier Analysis:

In addition to the analyses that are proportion-based, survival analysis will be performed (Kaplan-Meier estimate of survival function). Freedom from TLR at 30 days, 6 months, and 12 months: the time to first event will be the time from index-procedure to the first occurrence

of the first failure event, all subjects who have succeeded the TLR endpoint will be censored at Day 395 if not discontinued (discontinued subjects will be censored at discontinuation day), and all the subjects with missing TLR endpoint will be censored at the last available study day.

Binary outcome and Kaplan-Meier analyses for ATK, BTK and All UltraScore[™] subjects will be provided for the ITT population.

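### Protocol 6.5 allows participation to end before the 12-month contact for non-compliance or loss of contact, and no status follow-up for TLR, amputation or death is planned afterwards

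*Protocol*

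**What the plan says.** Protocol 6.5 starts from retention: "subjects should remain in the study until completion of required follow-up". It then lists grounds for ending participation early. Two of them involve neither withdrawal of consent nor risk to the subject.

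- **Non-compliance.** "the Investigator may terminate a subject's participation with prior written approval from the Sponsor if the subject is repeatedly noncompliant with study procedures". No failed contact is required.
- **Loss to follow-up (LTF).** A subject may be LTF if the site is "unable to locate the subject despite two documented attempts to notify the subject via telephone and a third attempt by certified mail". A missed contact followed by a completed one does not count, but "when a subject misses two consecutive follow-ups with failure of contact attempt, the subject may be considered LTF and withdrawn from the study". There is a safeguard: "Before the site considers a subject LTF, written agreement should be obtained from the Sponsor".

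Protocol 6.4 sets three contacts, at 30 days, 6 months and 12 months, and says that "study participants will either return to the site or be reached by telephone at the following intervals". At each contact the site records whether TLR, TVR or amputation has occurred since the last one. ATK subjects must also attend for duplex ultrasound.

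In the SAP, sections 6.2 (TLR) and 6.3 (major amputation) count an event-free subject at 12 months only if followed past Day 335. In the Kaplan-Meier analyses, "discontinued subjects will be censored at discontinuation day". Protocol 7.3 bases rates on available data without imputation. Neither document plans a sensitivity analysis for discontinued subjects.

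**The concern.** Stopping study tests and leaving the study are different things, and Protocol 6.5 does not separate them. An ATK subject who repeatedly declines ultrasound can be removed even though a telephone call would still establish whether a TLR or an amputation has occurred. A subject who misses the first two contacts and cannot be reached can be withdrawn with half the follow-up still to run, and no attempt at 12 months is then called for.

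Twelve months is the last time point for freedom from TLR and major amputation, which Protocol 2.2 names among the purposes of the study. Censoring at discontinuation is valid only if leaving is unrelated to later risk. People who skip tests or drop out of contact may differ in illness, limb status or place of care. That is a reasonable inference, but the documents give no figure for it. There is no control arm in which similar losses might offset the effect. Vital status is exposed too: Protocol 8.5 requires reporting of deaths during the study, while SAP 7.3.3 plans 12-month freedom from death in subjects treated with a drug-coated balloon.

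**Working it through.** The plan gives no figure to reproduce. Protocol 7.2 says that the sample size has no statistical basis, and no dropout or event rate appears anywhere.

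**Step 1: when each route can act before 12 months.**

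| Pattern | Before the 12-month contact? | Failed contact needed? | Sponsor sign-off? |
|---|---|---|---|
| Repeated non-compliance | Yes, at any time | No | Prior written approval |
| 30-day and 6-month contacts missed | Yes | Yes | Written agreement |
| 6- and 12-month contacts missed | No, completes at the end of follow-up | Yes | Written agreement |
| One miss, next contact completed | Not LTF | n/a | n/a |

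**Step 2: illustrative size for TLR.** Assumptions, none from the documents:
- 12-month TLR is 15% or 25% with a constant hazard λ.
- A share w of those event-free at 6 months is withdrawn then.
- From 6 months the hazard in the withdrawn is HR times that of the others, with HR 1.5 to 3.

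Write S6 = exp(-λ/2) and E = exp(-λ·HR/2).

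- True freedom at 12 months = S6 × [(1-w)·S6 + w·E]
- Kaplan-Meier value = S6 × S6
- Kaplan-Meier excess = w × S6 × (S6 - E)
- Binary value = (1-w)·S6² / (1 - w·S6), because SAP 6.2 keeps earlier events and drops event-free leavers

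For 15% TLR, λ = 0.1625 and S6 = 0.922. For 25% TLR, λ = 0.2877 and S6 = 0.866. At w = 10%:

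- Lowest Kaplan-Meier excess (15% TLR, HR 1.5): 0.10 × 0.922 × (0.922 - 0.885) = 0.3 points.
- Highest (25% TLR, HR 3): 0.10 × 0.866 × (0.866 - 0.650) = 1.9 points.
- Binary value at 25% TLR: 0.90 × 0.75 / (1 - 0.0866) = 73.9%. The true values are 74.5% (HR 1.5), 74.0% (HR 2) and 73.1% (HR 3), so the errors are -0.6, -0.1 and +0.8 points.
- At 15% TLR the binary errors are -0.4, -0.1 and +0.5 points.

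Kaplan-Meier excess by share withdrawn, over the same ranges of TLR and HR:

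| w | Excess (points) |
|---|---|
| 2% | 0.1-0.4 |
| 5% | 0.2-0.9 |
| 10% | 0.3-1.9 |
| 15% | 0.5-2.8 |

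**Step 3: what a bounding analysis would show.** Take N = 350, 35 subjects with unknown outcome, and 20% TLR among the other 315 (63 events). The planned estimate is 252/315 = 80.0% (exact 95% CI 75.2-84.3). If all 35 had a TLR it is 252/350 = 72.0%; if none did, 287/350 = 82.0%. The lower bound lies below the confidence interval.

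**The case against.** The case against is substantial, and much of it stands.

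- **The LTF route is narrow.** It needs two consecutive misses, failed telephone and certified-mail attempts, and sponsor agreement, and it is permissive. For someone who cannot be located, 12-month data are only potentially obtainable. A reader might infer that two missed contacts alone lead to withdrawal, or that the data are certainly lost. The text supports neither.
- **TLR is more than a telephone item.** Protocol 6.4 sends re-intervention angiograms to the core laboratory. SAP 6.2 does, however, accept the site's record when core-laboratory data are missing, so status obtained by telephone or from records would still be usable. Record searches depend on a consent form that is not part of these documents.
- **The direction is not fixed.** A reader might infer that the plan flatters the device. Under the assumptions above that holds for Kaplan-Meier. The binary rule errs the other way until the hazard ratio is somewhat above 2.
- **The model is a simplification.** It takes withdrawn subjects as observed to 6 months, whereas an LTF subject who missed both contacts has no contact-based status after discharge. Suppose nothing is known of 35 such subjects and their whole 12-month risk is 2 or 3 times the 20% in the others. The full-cohort value is then 78.0% or 76.0%, against a planned 80.0%. With 2% withdrawn (7 subjects) the gap is 0.4 or 0.8 points.
- **The study is descriptive.** There is no hypothesis, and SAP 9.7 reports discontinuations by reason, so their number will be visible.
- **Sponsor sign-off limits site discretion.** A reader might instead see it as sponsor influence over results, but the documents offer no evidence of that. Sign-off does not, however, retain any data.

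None of this answers the non-compliance route, where a reachable subject's outcome can be given up.

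**Conclusion.** The point holds within limits. Protocol 6.5 permits early exit without withdrawal of consent or a safety reason, and nothing in either document continues status follow-up afterwards. Obtainable TLR, amputation and vital status are given up under the non-compliance route and may be under the LTF route.

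The effect falls on the 12-month secondary endpoints and on survival in the drug-coated-balloon subgroup. Both primary endpoints are settled at the index procedure and are untouched.

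The size is unknown. The 0.3-1.9 point Kaplan-Meier overstatement rests on an assumed 10% withdrawn, 15-25% TLR and a hazard ratio of 1.5-3; it is under 1 point at 5% or fewer withdrawn. The binary estimate may be wrong in either direction, by about -0.6 to +0.8 points in the same model. This is an inexpensive improvement that should be made, not a flaw that undermines the study.

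**What to change.** **Protocol 6.5.** State that non-compliance or missed contacts end only the on-site tests. TLR, major amputation and vital status continue to be sought by telephone and, where the consent allows, by record review to the end of the 12-month window (Day 395), unless consent is withdrawn. Declare LTF only after the 12-month contact attempts have failed. Leave the safety ground for withdrawal unchanged.

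**SAP 6.2 and 6.3.** Add a bounding sensitivity analysis for 12-month TLR and major amputation, counting all and then none of the discontinued event-free subjects as having had an event. This remains feasible if follow-up has already ended.

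**Cost.** A protocol amendment with IRB review, possibly re-consent if record review is not already covered, a few extra calls or record checks per non-attending subject, and one additional table.

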7 STATISTICAL ANALYSIS PLAN

This section describes the planned statistical analyses for this study. A detailed Statistical Analysis Plan (SAP) will be completed and placed on file prior to database lock. The SAP will contain a comprehensive explanation of the methodology used in the statistical analyses described below.

7.1 Study Hypothesis

There is no formal statistical hypothesis for this study.

7.2 Sample Size Considerations

This study will enroll up to a maximum 350 subjects at approximately 35 sites. The sample size is based on potential adequacy of data to meet the study objectives; it is not based on any statistical consideration.

7.3 Data Analysis

The analysis population consists of all enrolled subjects who have signed the Informed Consent Form and have been treated with the study device.

Study endpoints will be summarized using descriptive statistics. Summary statistics for categorical variables will include frequency counts and percentages and for continuous variables mean, standard deviation, minimum, median and maximum.

Primary endpoints will be reported by rate and with a 95% confidence interval. The calculation of rates will be based on available data. Missing data will not be imputed.

7.4 Evaluation of Primary Endpoints

Primary endpoints are:

- Achieve optimal PTA results (≤30% residual stenosis, without flow limiting dissection)
- Achieve technical success of use where the UltraScore[™] Focused Force PTA balloon is delivered to the target lesion and inflated without movement

7.5 Evaluation of Secondary Endpoints

The following secondary endpoints will be reported at the index procedure or through 12 months at these time points: 30 days, 6 months, and 12 months.

After UltraScore[™] Focused Force PTA balloon:

• Rate of bail-out stenting due to dissection

Through follow-up (30 days, 6 and 12 months):

- Freedom from TLR
- Freedom from major amputation (above the ankle)
- Improved clinical measures from baseline (ABI, Rutherford)
- Primary patency for ATK subjects only (as measured by DUS core lab; a PSVR ≥2.5 suggests 50% restenosis)

7.6 Other Analyses

- Target lesion characteristics (e.g. location, type)
- Procedure details (e.g. duration, inflation times, inflation pressures, number of inflations to efface/dilate the target lesion)
- Adjunctive therapies before and after UltraScore use

7.7 Subgroup Analyses

- Primary and secondary endpoints will be explored between above the knee (ATK) and below the knee (BTK) subjects
- Primary and secondary endpoints will be explored between different adjunctive treatments

8 ADVERSE EVENTS AND DEVICE DEFICIENCIES

The PI is responsible for the detection, documentation and reporting to the Sponsor of events meeting the criteria and definitions set forth in this Section. Collection and reporting of AEs/SAEs will be limited to those events that are device and/or procedure related as outlined below and reporting will begin immediately following subject enrollment, during the index procedure.

8.1 Definitions of Events

8.1.1 Definition of Adverse Events (AEs)

Collection of AEs will be limited to those that are associated with a localized or systemic clinical manifestation that reasonably suggests the involvement of the UltraScore device and/or procedure.

- Device-Related: This category should be restricted to AEs directly attributable to the UltraScore[™] Focused Force PTA balloon device used as part of the procedure.
- Procedure-Related: This category should be restricted to AEs directly attributable to the portion of the procedure when the UltraScoreTM Focused Force PTA balloon is used, including insertion, inflation, deflation and removal of the balloon. AEs that arise from arterial access and adjunctive therapies (preand post-UltraScore use) should not be reported in this study.

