8.3 Relationship of Adverse Event to Device(s)/Procedure

Investigators will assess each AE for its relationship to the device or procedure. The following categories should be used for assigning the certainty of the relatedness:

- *Definitely Related:* An AE is definitely related if it is obvious, certain or there is little doubt regarding the relationship.
- *Possibly Related:* An AE is possibly related if it is capable of being related but relatively unlikely.
- *Not Related:* An AE is not related if it is determined that there is no plausible association.

Potential adverse events which may be associated with peripheral balloon dilatation with the UltraScore balloon are found in the IFU.

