8.4 Reporting of Events

All AEs determined to be related to the device/procedure, should be recorded on the appropriate eCRF.

It is the responsibility of the Investigator to notify the IRB of applicable AEs in accordance with the governing IRB requirements.

See section 11.7 for all study reporting requirements.

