8.1 Adverse Events (AEs)

Collection of AEs will be limited to those that are associated with a localized or systemic clinical manifestation that reasonably suggests the involvement of the UltraScoreTM device and/or procedure. Adverse Events (AEs) experienced by the subject will be collected from the time point of enrollment until the subject's end of study participation. Event occurred prior to enrollment will be documented as medical history. All adverse events occurring in this study will be classified in accordance with the adverse event signs or symptoms and will be coded using the Medical Dictionary for Regulatory Activities (MedDRA). AEs will be summarized by system organ class and preferred term.

The number and percentage of subjects with at least one AE, total number of AEs, AEs by relationship to the device/procedure, and AEs by severity of the event will be summarized by ATK, BTK and All UltraScoreTM subjects using site-reported data. A summary of SAE will be provided. A listing of all AEs, as well as of the SAEs, will be provided.

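### Protocol 8, 8.1.1, 8.3 and 8.4 and SAP 8.1 set inconsistent attribution thresholds for AE collection, so AE and SAE rates may be under-ascertained and may vary by site

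*Protocol*

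**What the plan says.** Protocol section 8 makes AE and SAE collection selective: it is "limited to those events that are device and/or procedure related as outlined below". What is outlined below it comes in several parts.

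- **Protocol 8.1.1, lead sentence:** AEs are collected if they are associated with a clinical "manifestation that reasonably suggests the involvement of the UltraScore device and/or procedure". SAP 8.1 repeats this rule and does not use the narrower wording of the bullets.
- **Protocol 8.1.1, bullets:** there are two categories, device-related and procedure-related. For both, the text reads "This category should be restricted to AEs directly attributable to the" balloon, or to the portion of the procedure in which it is used. The second bullet adds that "AEs that arise from arterial access and adjunctive therapies" "should not be reported in this study".
- **Protocol 8.1.2:** an SAE must first satisfy the AE definition.
- **Protocol 8.3:** the investigator grades each AE as definitely, possibly or not related. The top level needs little or no doubt. For the middle level, "An AE is possibly related if it is capable of being related but relatively unlikely". The lowest level means no plausible association.
- **Protocol 8.4:** "All AEs determined to be related to the device/procedure, should be recorded on the appropriate eCRF". It does not say which 8.3 levels count as related.
- **SAP 8.1:** "AEs by relationship to the device/procedure, and AEs by severity of the event will be summarized" from site-reported data, for ATK, BTK and all subjects. Neither document describes independent adjudication of AEs.

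**The concern.** These rules decide which events enter the AE data, and they do not agree. An event that is relatively unlikely to be related cannot also be directly attributable to the balloon. A site that takes the 8.1.1 bullets as its entry rule leaves such an event out. A site that follows the 8.1.1 lead sentence, or reads 8.3 as listing what may be entered, puts it in. Both can say that they followed the protocol.

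The events affected are those of uncertain cause. They should not be rare in principle here, because adjunctive treatment of the same lesion is allowed before or after UltraScore (Protocol 6.2.1). At stake are the AE and SAE tables in SAP 8.1. If the narrow reading is used, their rates can only be lower. If sites differ in their reading, the pooled rate mixes two definitions in unknown proportion. The narrow reading reaches serious events too, because an SAE must first be an AE.

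**Working it through.** **1. No planned figure to reproduce.** The protocol and SAP give no expected AE rate, no precision target and no hypothesis (Protocol 7.1, 7.2). The check is therefore of the text, followed by an illustration.

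**2. One event traced through each rule.** Take a distal embolus seen after both UltraScore and an adjunct have been used on the target lesion, with cause uncertain.

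| Rule | Is the event entered? |
|---|---|
| Protocol 8.1.1 lead sentence; SAP 8.1 | Yes, if balloon involvement is reasonably suggested |
| Protocol 8.1.1 bullets | No, it is not directly attributable to the balloon or its use |
| Protocol 8.1.1, adjunct exclusion | No, if the site assigns it to the adjunct |
| Protocol 8.3 | Can be graded 'Possibly related', which presumes that such events are entered |
| Protocol 8.4 | Undetermined, since 'related' is not tied to a level |

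The answer depends on which sentence the site reads as governing. One site may enrol up to 20% of subjects, so a single site's reading could apply to as many as 0.20 × 350 = 70 subjects.

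**3. The gap in the scale.** In order of certainty, 8.3 runs: no plausible association; capable but relatively unlikely; little or no doubt. An event that is more likely than not due to the balloon, but with real doubt, is neither 'relatively unlikely' nor beyond doubt. It fits no level.

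**4. What does not depend on this rule.** Death for any cause is reported (Protocol 8.5). TLR, TVR and amputation are asked about at every follow-up contact (Protocol 6.4). Grade D to F dissection is collected (Protocol 6.2.3) and analysed from core-lab data with site data as back-up (SAP 5.1). Bail-out stenting has its own CRF source (SAP 6.1). None of the primary or secondary endpoints uses the AE form.

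**5. Illustration of size.** All counts here are assumptions. Let *c* be subjects with a clearly attributable AE, and *p* be subjects whose only AEs are possibly related. With N = 350:

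- narrow reading: rate = *c* / 350
- wide reading: rate = (*c* + *p*) / 350

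| *c* | *p* | Narrow (exact 95% CI) | Wide (exact 95% CI) |
|---|---|---|---|
| 7 | 0 | 7/350 = 2.0% (0.81 to 4.08) | 7/350 = 2.0% (0.81 to 4.08) |
| 7 | 7 | 2.0% | 14/350 = 4.0% (2.20 to 6.62) |
| 7 | 14 | 2.0% | 21/350 = 6.0% (3.75 to 9.03) |
| 7 | 21 | 2.0% | 28/350 = 8.0% (5.38 to 11.35) |
| 14 | 21 | 14/350 = 4.0% (2.20 to 6.62) | 35/350 = 10.0% (7.06 to 13.63) |

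The difference is *p* / 350, so it runs from 0 to 21/350 = 6.0 percentage points over this range. If half of the possibly related subjects were entered, the rate would fall midway. For *c* = 7 and *p* = 21 that is (7 + 10.5)/350 = 5.0%.

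**The case against.** The strongest reply is that the rules can be read together. The 8.1.1 lead sentence governs collection, and SAP 8.1 adopts it. The bullets then only sort events by source (balloon, or the UltraScore part of the procedure), and 8.3 grades certainty, which is a separate axis. On that reading possibly related events are collected and nothing is lost. This is a fair reading, and it is why under-reporting cannot be stated as fact. It does not remove the problem. The bullets use the language of causal certainty, section 8 limits collection to related events as outlined below it, and 8.4 leaves 'related' open, so the narrow reading is equally compliant.

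A second reply is that this is an observational study of a cleared device used on label. Collecting only related events, and excluding those from access and adjuncts, is a deliberate limit on scope. That stands. The point here is that 'related' has incompatible definitions, and it is no argument for recording every target-limb event whatever its cause.

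A reader might also infer that the 'Not related' level must be empty because only related events are recorded. The documents do not establish this. If device and procedure are rated separately, which the text allows, an event can be procedure-related and not device-related.

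A reader might further infer that the study's safety findings as a whole are unreliable. That goes too far, since death, re-intervention, amputation and major dissection are captured whatever their attribution.

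**Conclusion.** The thresholds in Protocol 8, 8.1.1, 8.3 and 8.4 and SAP 8.1 are inconsistent, and the 8.3 scale has a gap between its middle and top levels. It is unclear whether possibly related events are reported. The AE and SAE rates in SAP 8.1 may therefore be under-ascertained and may vary by site. The direction under the narrow reading can only be downward.

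The size cannot be found from the documents. On the assumed counts with 7 clear-event subjects, the rate lies between 2.0% and 8.0%, and the shift is zero if no subject has only possibly related events. It is tempting to say that ambiguous events go unreported and that the AE rate is too low. The documents support only a risk of this, because the wider rule also stands in both of them.

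The effect is confined to the AE and SAE tables. The point should be corrected, but it does not touch the primary or secondary endpoints.

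**What to change.** Use one threshold throughout:

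1. **Protocol 8.1.1:** in both bullets, replace the 'directly attributable' condition with wording that matches the lead sentence and the 8.3 scale, namely definitely or possibly related.
2. **Protocol 8.3:** redefine 'Possibly related' to cover every plausible link short of the top level, or add a level between the two, so that no event is without a category.
3. **Protocol 8.4:** state that every level other than 'Not related' is recorded.
4. **SAP 8.1:** report the percentage of subjects with an AE, and with an SAE, twice: for definitely related events, and for definitely or possibly related events. If a level is added in 8.3, count it in the second rate.

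The exclusion of access and adjunct AEs may stay, provided that an event whose cause is uncertain between UltraScore and an adjunct is recorded as possibly related.

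The SAP, dated January 2022, already deals with 12-month visits delayed by COVID-19, so changes to collection may come too late. If data collection is complete, make the SAP split and state as a limitation that sites may have applied different entry thresholds. The split cannot restore events that were never entered on an AE form.

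The cost is wording in the protocol and SAP, a few more AE forms if collection is still open, and a reported AE rate that may be higher.
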